performed in 158 (79.8%) and 40 (20.2%) patients, respectively. Sixteen (8%) patients underwent unilateral central lymph node dissection (CLND) additional to total thyroidectomy. Age, gender, body mass index (BMI), the indications for surgery, presence of hyperthyroidism, evidence of autoimmune thyroid disease (ATD) and thyroid lobe volume were recorded in all patients, preoperatively. Thyroid lobe volume was calculated by using the dimensions (length(L), width(W), thickness(T)) of each thyroid lobe measured by ultrasonography according to the following formula; $\pi/6 \times L \times W \times T^{18}$.

All NAR's were dissected by using CIONM including vagal response evaluation at the beginning and at the end of the operation (IONM = L1,V1, R1, R2,V2, L2) according to the recommendations by the International Intraoperative Neural Monitoring Study Group ⁷. All patients underwent pre-, and postoperative laryngoscopic examination within 2 days after surgery, and repeated serially if abnormal (L1, L2). All operations were performed by experienced endocrine surgeons. Length of RLN dissection was defined as extended if the nerve was dissected for 5 cm or greater. Duration of lobectomy for each site, period of time for initial identification of RLN after the mobilization of upper pole on each site, the relationship of the RLN to the ligament of Berry (LOB) and to the Tubercl of Zuckerkandl (TZ) (if present), extralaryngeal branching of the RLN, length of RLN dissection, presurgery and postsurgery amplitude and latency of the vagus and the RLN, occurrence of adverse EMG changes and recovery time or loss of signal (LOS) were recorded intraoperatively in all patients. Serum levels of calcium and parathormone on the first postoperative day were analyzed in all patients. The rates of post-thyroidectomy hypoparathyroidism and vocal cord palsy (VCP) were recorded. Final histopathological diagnosis was documented in all patients, postoperatively.

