Demographic data, BMI, the indications for surgery, clinicopathological features, thyroid volume, duration of the operation, period of time for RLN identification, anatomical variations, length of RLN dissection, presurgery and postsurgery amplitude and latency of the vagus and RLN, the rate of adverse EMG changes, LOS and morbidity (vocal cord palsy, hypoparathyroidism) were compared between group 1 and 2. The correlation between intraoperative adverse EMG changes and anatomic variations, lobe volume and type of thyroid disease was investigated as well.

Thyroid surgery and CIONM technique

All operations were performed under general anesthesia by using a small dose (0.3 mg/kg) of non-depolarizing muscle relaxant (Esmeron; MSD Sharp & Dohme GmbH, Haar, Germany) at intubation. The endotracheal tube was properly inserted to ensure that the recording surface electrode was placed at the level of the vocal cords. Prior to lobectomy, the carotid sheath was carefully dissected and the vagus nerve was identified using a hand held stimulation probe. The vagus nerve was dissected over a distance of ≤ 1 cm to place the vagus electrode. (automated periodic stimulation (APS) (Medtronic Xomed, Jacksonville, FL) or saxaphone probe (vagus electrode) ([name] GmbH, Avalanche SI, Germany).

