The baselines for latency and amplitude were automatically calibrated after the connection of the vagus electrode with the neuromonitoring system. CIONM had been carried out with one of the two following commercially available neuromonitoring devices: (1) NIM 3.0 Nerve Monitoring Systems; Medtronic Xomed, Jacksonville, FL; or (2) [name] GmbH, Avalanche SI, Germany. Achievement of initial presurgical dissection amplitude of $\geq 500\mu\text{V}$ was aimed in all patients. During the operations, adverse EMG parameters were defined as amplitude decrease of 50% or more of baseline value and/or latency increase of 10% or more ¹¹. A combined event (CE) was defined as concordant amplitude decrease of more than 50% and latency increase of more than 10%, regarding to baseline values ¹¹. The surgical maneuver was immediately altered and the traction released if adverse EMG changes were noted during surgery and waited to achieve the recovery of EMG changes. Recovery was defined as amplitude recovery to $>50\%$ of the initial baseline amplitude. Loss of signal (LOS) was defined as amplitude $<100\mu\text{V}$ ¹⁹. In case of LOS during the surgery of initial site, contralateral surgery was aborted if the amplitude did not recover to greater than 50% of the initial baseline amplitude within 20 minutes of the initial decline. During surgery, isthmus was divided first in both group of patients. Then the upper lobe of the gland was dissected through the avascular zone between the upper lobe and the cricothyroid muscle. The external branch of the superior laryngeal nerve was identified visually and, or by using neuro-monitoring hand probe prior to dissection of the upper pole vessels, and then the branches of upper pole vessels were ligated individually. Identification and preservation of all parathyroid glands and their vascular supply was tried in all cases. In case of incidental parathyroidectomy or totally compromised vascularity of the parathyroid glands, autotransplantation in to sternocleidomastoid muscle was performed.

RLN identification

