Lateral approach: Following the ligation of upper pole vessels, the thyroid lobe was pulled anteromedially and the RLN was seeked within the carotid triangle at the level of inferior thyroid artery (ITA). The tissue between the carotid artery and the trachea was dissected gently parallel to the direction of the nerve until the nerve is identified visually and by hand held stimulation probe. After the identification of RLN, the vessels of inferior thyroid lobe was ligated. The nerve was dissected along its course to the entry point, and then the thyroid lobe was totally dissected from the trachea and the lobectomy was completed. If adverse EMG changes were encountered during lateral approach, traction was released immediately and waited for recovery. If the adverse EMG changes recovered, RLN dissection was proceeded by lateral approach again. If the adverse EMG changes did not recover after traction release or in case of repeated adverse EMG changes, lateral approach was abandoned. The thyroid lobe was retracted laterally and medial aspect of the lobe was dissected from the trachea. The RLN dissection was continued by medial approach in such cases.

Cranio-caudal approach: Following the ligation of upper pole vesels, the upper pole was retracted antero-medially to expose crico-pharyngeal muscle. The RLN was identified at the point of entry both visually and with hand held stimulation probe. The RLN dissection was proceeded craniocaudally by the division of the suspensory ligaments of the LOB through the level of ITA. After the identification and visualization of the RLN through its whole course, the medial and inferior vessels of the thyroid gland were dissected and ligated. Then, the lobe was dissected from the trachea and lobectomy was completed. If adverse EMG changes were encountered during cranio-caudal approach, traction was released immediately and waited for recovery. The RLN dissection was proceeded by cranio-caudal fashion again if the EMG changes recovered. If the EMG changes did not recover or in case of repeated adverse EMG changes, cranio-caudal approach was abandoned and RLN was dissected by lateral approach. If repeated adverse EMG changes were encountered despite conversion from cranio-caudal to lateral approach, then the lobe was retracted laterally and medial aspect of the lobe was dissected from the trachea. The RLN was dissected by medial approach in such cases with repeated adverse EMG changes.

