Date: 1 March 2020

Study Name: Comparison Of The Incidence Of Recurrent Laryngeal Injury Following The Dissection Of The Nerve By Cranio-Caudal And Lateral Approach By Using Introperative Nerve Monitoring

Statistical Analysis Plan: The Statistical Package for Social Sciences (SPSS) for Windows Version 21.0 (Armonk, NY: IBM Corp.) was used for statistical analysis. The continuous variables are summarised as mean \pm standard deviation. The differences between the groups were assessed using the Student's t-test and a Mann-Whitney U test for normally distributed and non-normally distributed data, respectively. Univariate analysis by Chi-square test was performed to test differences in proportions. Statistically significant results obtained from the univariate analysis were subjected to multivariate logistic regression. A p value <0.05 was considered to be statistically significant.

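### The comparison of postsurgery vagus and RLN amplitude and latency has no described baseline adjustment, although presurgery values were recorded

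*Protocol*

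**What the plan says.** The Protocol's Study Design text states that "presurgery and postsurgery amplitude and latency of the vagus and the RLN" were recorded during the operation in all patients. The later list of between-group comparisons names them again: "presurgery and postsurgery amplitude and latency of the vagus and RLN, the rate of adverse EMG changes, LOS and morbidity".

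The SAP assigns continuous data to Student's t-test and a "Mann-Whitney U test for normally distributed and non-normally distributed data, respectively". Its only adjusted analysis is this: "Statistically significant results obtained from the univariate analysis were subjected to multivariate logistic regression". It mentions no ANCOVA, change score or percentage-of-baseline analysis. It also does not say whether the tests were applied to raw values or to changes. Separate tests of the presurgery and postsurgery values are the natural reading, but that is an inference.

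Three statements bear on which presurgery value precedes the randomised approach:

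- **Vagus, placement.** Under Thyroid surgery and CIONM technique: "Prior to lobectomy, the carotid sheath was carefully dissected and the vagus nerve was identified using a hand held stimulation probe". The electrode is then placed.
- **Vagus, baseline.** In the same section: "The baselines for latency and amplitude were automatically calibrated after the connection of the vagus electrode with the neuromonitoring system". The Study Design text also describes "vagal response evaluation at the beginning and at the end of the operation", and its testing sequence puts V1 before R1.
- **RLN.** Under RLN identification, lateral approach, the tissue "was dissected gently parallel to the direction of the nerve until the nerve is identified visually and by hand held stimulation probe". In the cranio-caudal arm the nerve is likewise found, visually and by probe, after the upper pole has been retracted.

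**The concern.** A two-sample test of a postsurgery value leaves in the error term all the between-patient variation that was already present before surgery. When a presurgery measurement of the same quantity exists, ANCOVA removes the part that it predicts. The SAP's logistic model needs a binary outcome, so it cannot do this for amplitude or latency.

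What is at stake is precision and power for a supportive comparison. Any baseline difference between the analysed arms would also carry through to the unadjusted postsurgery result, although the documents show no such difference.

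The choice of covariate needs care. The vagal value is obtained before the lobe is mobilised. The RLN's presurgery value is obtained only once the nerve has been exposed by the assigned route, so it may already reflect the approach. Adjusting for it could remove or distort part of the effect being estimated.

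**Working it through.** The plan states no sample size calculation, standard deviation, effect size or presurgery/postsurgery correlation, so there is no design figure to reproduce. Correlations and effect sizes below are assumptions.

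**Inputs from the Protocol (Study Design).** Randomised: 121 lateral, 112 cranio-caudal. Excluded after randomisation for equipment failure or a presurgical amplitude below 500 µV: 9 and 26. Analysed: 121 − 9 = 112 and 112 − 26 = 86, total 198. Total thyroidectomy 158, lobectomy 40. The SAP gives alpha 0.05; I assume two-sided.

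**1. Unadjusted precision, one value per patient.** SE = SD × √(1/112 + 1/86) = 0.143 SD. The difference detectable with 80% power is (1.960 + 0.842) × 0.143 = 0.40 SD.

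**2. Effect of adjustment.** ANCOVA multiplies the variance by 1 − ρ². For comparison, a change score multiplies the SE by √(2(1 − ρ)), assuming equal SDs before and after.

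| ρ (assumed) | Variance ratio | Variance cut | Equivalent unadjusted N, 198/(1 − ρ²) | Change-score SE factor |
|---|---|---|---|---|
| 0.3 | 0.91 | 9% | 218 | 1.18 |
| 0.5 | 0.75 | 25% | 264 | 1.00 |
| 0.7 | 0.51 | 49% | 388 | 0.77 |

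A change score therefore gains nothing at ρ of 0.5 or below, and ANCOVA is the relevant method.

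**3. Allowance for the 500 µV exclusion (amplitude only).** At most (9 + 26)/233 = 15.0% of randomised patients were removed for low amplitude, because that reason is pooled with equipment failure. By arm the total is 9/121 = 7.4% and 26/112 = 23.2%. Cutting the lowest 15% from a normal (log-scale) baseline gives:

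- c = −1.036
- λ = φ(c)/0.85 = 0.274
- remaining variance v = 1 + cλ − λ² = 0.640
- ρ_t = ρ√v / √(1 − ρ²(1 − v)) = 0.244, 0.419, 0.617
- variance cut ρ_t² = 6%, 18%, 38%

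**4. Rank-based branch.** Simulation with 112 v 86, one value per patient and an assumed true difference of 0.40 SD:

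| | Mann-Whitney power | Rank ANCOVA power at ρ = 0.3 / 0.5 / 0.7 |
|---|---|---|
| No cut-off | about 78% | 80% / 87% / 96% |
| Lowest 15% removed | 78–79% | 80% / 84% / 92% |

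Simulated type I error stayed between 0.044 and 0.056. A separate run of 3,000 replicates agreed to within about 3 percentage points.

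**5. Two nerves per patient.** There are up to 2 × 158 + 40 = 356 nerves. With an assumed within-patient correlation of 0.3 and a mean of 356/198 = 1.80 nerves per patient, the design effect is 1 + 0.80 × 0.3 = 1.24 and the effective N is 356/1.24 = 287. Split 112:86, this gives SE ≈ 0.119 SD. At 0.40 SD, normal-theory power is about 92% unadjusted, 94% at ρ = 0.3 and 97% at ρ = 0.5.

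**6. Why the vagal covariate.** If approach-specific exposure shifted the presurgery RLN value by an assumed 0.2 SD, adjusting for that value would move the estimated difference by ρ × 0.2 = 0.06, 0.10 or 0.14 SD.

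**The case against.** The strongest reply is that nothing here is invalid. In a randomised comparison an unadjusted t-test or Mann-Whitney test is legitimate, and the same remark could be made of almost any trial with a measurement before and after. The outcome is peripheral: RLN injury is primary, the named secondary endpoints concern predictors of that injury, and raw amplitude and latency sit in a long list of compared variables. Baseline is not ignored either, since adverse EMG change, combined event and recovery are all defined against it. All of this stands, and it is why the point is minor. Those baseline-referenced measures are dichotomies, however, and do not adjust the separate postsurgery comparison that the Protocol lists.

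The power figures are also fairly criticised. They rest on an assumed correlation and on an effect size chosen where gains show clearly. At 0.50 SD and ρ = 0.5, normal-theory power only rises from 94% to 98%. Counting nerves rather than patients shrinks the gain further (step 5), and a common 15% cut-off ignores the unequal exclusions. The percentage variance cuts are the sturdier summary.

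On the remedy, that the RLN baseline may reflect the approach is inferred from the order of the surgical steps. The vagal value may also predict RLN outcomes less well. For second sides, the Protocol does not say whether the vagal baseline was set before or after the first side was dissected, and second-side values exist only where surgery continued. The same-side vagal value still precedes the approach-specific dissection of that side, so it remains the safer covariate.

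**Conclusion.** The concern holds as a minor, optional improvement. The documents describe no baseline adjustment for a comparison that they list, and a suitable covariate was already collected. The unadjusted tests are not wrong; they are less efficient if the presurgery and postsurgery values correlate.

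The loss depends on a correlation that the documents do not give. It is negligible near 0.3 (a 6–9% variance cut) and material from about 0.5 (18–25%), reaching 38–49% at 0.7. The lower figure in each range applies to amplitude if the 500 µV rule removed 15% of baselines. For RLN outcomes adjusted for the vagal value the gain is probably smaller and cannot be quantified. No baseline imbalance is claimed, and the primary endpoint is untouched. Confidence is medium.

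**What to change.** Add a few sentences to the SAP:

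- **Vagal outcomes.** Analyse each postsurgery vagal amplitude and latency by ANCOVA on randomised arm plus the matching presurgery vagal value.
- **RLN outcomes.** Use the presurgery vagal value of the same side and the same measure as the main covariate. Adjust for the presurgery RLN value only as a sensitivity analysis.
- **Scale.** Use a log or rank scale where values are not normal. Zero amplitudes after loss of signal could not be logged and would call for ranks.
- **Clustering.** Use standard errors clustered by patient where two nerves contribute. If the order of the sides was recorded, repeat the analysis on first sides only.
- **Reporting.** Give the adjusted difference (a ratio on the log scale) with a 95% CI, and show presurgery values by arm descriptively. State whether the existing tests used raw values or changes.
- **Status.** Label the analysis supportive and post hoc. Both documents are dated 1 March 2020, after the June 2018 to November 2019 referral period.

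The cost is slight extra analysis and no new data. A scale has to be chosen, and the vagal covariate may be a weaker predictor than the RLN's own baseline. Adjustment does not repair the 9 v 26 exclusions after randomisation.

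### The plan sets no common stimulation site for RLN latency, and the nerve is first reached at a different point in each arm, so the between-arm comparison of presurgery RLN latency cannot be read as nerve function alone

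*Protocol*

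**What the plan says.** The Study Design section of the Protocol gives the recording sequence as "IONM = L1,V1, R1, R2,V2, L2" and refers to an international recommendation for it. I take R1 and R2 to be the presurgery and postsurgery RLN readings. The same section lists what is compared between group 1 and group 2, including "presurgery and postsurgery amplitude and latency of the vagus and RLN, the rate of adverse EMG changes, LOS and morbidity".

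The RLN identification section describes how the nerve is reached:

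- **Lateral arm:** "the RLN was seeked within the carotid triangle at the level of inferior thyroid artery (ITA", with dissection continuing "until the nerve is identified visually and by hand held stimulation probe". After that, "The nerve was dissected along its course to the entry point".
- **Cranio-caudal arm:** "The RLN was identified at the point of entry both visually and with hand held stimulation probe". After that, "The RLN dissection was proceeded craniocaudally by the division of the suspensory ligaments of the LOB through the level of ITA".

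Under Thyroid surgery and CIONM technique, the vagus is exposed in the carotid sheath before lobectomy. One procedure is described for all patients, and the continuous-monitoring baseline is calibrated through the vagus electrode.

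The SAP compares continuous variables by Student's t-test or Mann-Whitney U at p < 0.05. It does not mention stimulation site. Neither document says where on the nerve, or at what step, R1 or R2 was stimulated.

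**The concern.** Latency includes the time the impulse takes to travel from the stimulating probe to the larynx, so it depends on where the probe is placed. The two approaches reach the nerve from opposite ends of the exposed segment: ITA level first in one arm, the entry point first in the other. A reading taken when the nerve is first found would therefore have a shorter conduction path in the cranio-caudal arm, and a shorter latency even if the nerves function identically.

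The shift would run in one direction, so a larger sample makes a spurious significant result more likely. The trial asks which approach is safer for the nerve, and a significant RLN latency difference could easily be read as evidence on that question.

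**Working it through.** **Step 1. Can R1 be both same-site and pre-dissection in both arms?** The documents give no latency values, SDs or design figure to reproduce, so the check starts from the described exposure sequence.

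| R1 read at | Lateral arm | Cranio-caudal arm | Consequence |
|---|---|---|---|
| First identification | ITA level | Entry point | Site differs by arm |
| ITA level in both | At first identification | After dissection from the entry point through the ligament of Berry | Prior dissection differs by arm |
| Entry point in both | After dissection along the nerve | At first identification | Prior dissection differs by arm |

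Each row leaves the comparison confounded with approach. Stimulating through undissected tissue could avoid this, but neither document describes it. By the end of the operation the segment from ITA level to the entry point is exposed in both arms, so R2 could have been read at a common site. Whether it was is not stated.

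**Step 2. How large could a pure site effect on latency be?** All inputs here are assumptions: 1-5 cm between the sites and a conduction velocity of 40-60 m/s.

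Shift (ms) = distance (mm) / velocity (m/s)

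| Distance | 40 m/s | 50 m/s | 60 m/s |
|---|---|---|---|
| 10 mm | 0.25 | 0.20 | 0.17 |
| 20 mm | 0.50 | 0.40 | 0.33 |
| 30 mm | 0.75 | 0.60 | 0.50 |
| 50 mm | 1.25 | 1.00 | 0.83 |

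The range is 0.17-1.25 ms. Against an assumed RLN latency of 2-4 ms, that is 4% (0.17/4) to 63% (1.25/2).

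**Step 3. Would the planned test pick it up?** The inputs from the Study Design section are 112 lateral and 86 cranio-caudal patients analysed. I assume a two-sided 0.05 test and one reading per patient.

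- Standard error in SD units = √(1/86 + 1/112) = 0.143.
- Shift significant half the time: 1.96 × 0.143 = 0.28 SD.
- Shift significant 80% of the time: (1.96 + 0.84) × 0.143 = 0.40 SD.

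Chance of a significant difference when nerve function is equal, for an assumed SD:

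| Shift | SD 0.5 ms | SD 1.0 ms | SD 1.5 ms |
|---|---|---|---|
| 0.17 ms | 66% | 22% | 12% |
| 0.40 ms | >99% | 80% | 46% |
| 0.60 ms | >99% | 99% | 80% |

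Even the smallest shift in the assumed range lifts the false-positive rate above the nominal 5%. These figures apply only if R1 was read at first identification. No comparable calculation is possible for amplitude, because the documents give no stimulation current and no relation between site and amplitude.

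**The case against.** The strongest reply is that the documents never say where R1 was stimulated. Identifying the nerve with a probe is not the same as recording the analysed value at that contact, and the cited recommendation, which is not available here, may set a site. This stands: a reader might infer that the arms were in fact read at different points, and the text does not establish that. It does not remove the problem, because a common site makes one arm's reading follow dissection (Step 1).

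Other objections also stand in whole or in part:

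- **Amplitude.** A reader might extend the argument to it. The mechanism is conduction distance, which bears on latency only.
- **Deterioration in one arm.** A reader might expect a false R1-to-R2 rise. Neither document plans a test of change, and a rise would also require R2 to be read further from the larynx than R1.
- **The 10% latency criterion.** It is tempting to set the shift against the Protocol's adverse-change threshold. That threshold is an intraoperative alarm that appears to rest on the vagal baseline, so it is not a criterion for R1 between arms.
- **Exclusions.** Intraoperative exclusions were 9/121 (7.4%) and 26/112 (23.2%), and a reader might attribute the imbalance to stimulation site. The counts pool equipment failure with low amplitude, and the documents do not say whether the 500 µV criterion refers to the vagus or the RLN.
- **Importance.** RLN latency is neither the primary endpoint nor a named secondary endpoint, and unaffected vagal readings are in the same comparison list.

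**Conclusion.** The concern holds in a limited form. On the described exposure sequence, no R1 latency is both same-site and pre-dissection in both arms, and no common site is set for R1 or R2. The between-arm comparison of presurgery RLN latency is therefore confounded either with stimulation site or with prior dissection.

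The size is unknown from the documents. A pure site effect would be about 0.2-1.25 ms under the assumed distances and velocities. Whether that reaches significance depends on an SD that the documents do not give.

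The results that answer the trial's main question are untouched: RLN injury, laryngoscopic vocal cord palsy and the vagal readings. Adverse EMG changes are also unaffected in so far as they rest on the vagal baseline, as they appear to. This is worth correcting because a spurious difference is possible and the correction is cheap, but it does not threaten the trial's main conclusion.

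**What to change.** - Base between-arm inference on latency on V1 and V2. Both are already recorded, and the vagus is exposed by the same described procedure in both arms.
- Report R1 latency, and any R1-to-R2 change, descriptively by arm without a between-arm test.
- State at which point on the nerve, and at which step of the operation, R1 and R2 were stimulated in each arm.
- Test R2 latency between arms only if the records document a common site.

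The Protocol is dated 1 March 2020 and gives the referral period as June 2018 to November 2019, with the analysed patients already counted. A fixed R2 landmark therefore cannot now be imposed; only analysis and reporting can change. The cost is some rewording of the comparison list and the SAP, and one non-endpoint RLN comparison becomes descriptive.

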Date: 1 March 2020

Study Name: Comparison Of The Incidence Of Recurrent Laryngeal Injury Following The Dissection Of The Nerve By Cranio-Caudal And Lateral Approach By Using Introoperative Nerve Monitoring

Study Design: This prospective study was approved by the institutional review board and informed consent was obtained from each patient . A total of 327 patients who were referred to undergo thyroid surgery between June 2018 and November 2019 were assessed for the eligibility to participate in the study. Of these, 233 were considered to be eligible for the study. Exclusion criteria included previous thyroid or parathyroid surgery, substernal goiter, preoperative VCP, evidence of lateral lymph node metastasis, intentional transection of the RLN due to tumor invasion, failure to assess RLN functioning due to equipment issues with the IONM setup, presurgical dissection amplitude of $<500\mu\text{V}$ and patient's refusal to participate in the study. Of 327 patients, 94 were excluded preoperatively due to previous neck surgery (n=47), evidence of lateral neck metastasis(n=24), patient's refusal (n=13) and presence of substernal goiter (n=10). The remaining 233 patients were randomized to have RLN's identified by lateral (n=121) or cranio-caudal approach (n=112 (Figure 1). Computer generated random numbers were generated and printed on cards. These cards were placed in sealed, opaque envelopes. On the morning of operation, one envelope was opened before the operation and, depending of the parity of the number, RLN's of the patient were dissected either by cranio-caudal or lateral dissection during the operation. The patients and the nerves at risk (NAR's) in the lateral and cranio-caudal approach groups were classified as group 1 and 2, respectively. In group 1 and 2, nine and twenty-six patients were further excluded, respectively, owing to intraoperative failure to assess RLN functioning due to equipment issues with the IONM setup or presurgical dissection amplitude of $<500\mu\text{V}$.

Thus, the data of 198 patients were analysed for primary and secondary outcome measures. The primary endpoint was RLN injury and the secondary endpoints included the effect of clinicopathological features, anatomic variations and adverse EMG changes on the occurrence of RLN injury. Of 198 patients, 112 were in the lateral approach group (group 1) and 86 in the cranio-caudal approach group (group 2). Total thyroidectomy or lobectomy was

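### Raw latency comparisons have no term for side or patient, so a pooled per-nerve test can have error bars that are too narrow or too wide (minor)

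*Protocol*

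**What the plan says.** The Study Design section of the protocol lists the variables to be compared between group 1 (lateral) and group 2 (cranio-caudal). The list includes "presurgery and postsurgery amplitude and latency of the vagus and RLN".

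The SAP has one rule for continuous variables: "The differences between the groups were assessed using the Student's t-test and a Mann-Whitney U test for normally distributed and non-normally distributed data, respectively". The threshold is also stated: "A p value <0.05 was considered to be statistically significant". No covariate, stratum or clustering term is attached to either test. Logistic regression is reserved for significant univariate results and does not apply to a latency comparison.

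Two statements bear on the unit of analysis. First, "The patients and the nerves at risk (NAR's) in the lateral and cranio-caudal approach groups were classified as group 1 and 2, respectively", so nerves as well as patients carry a group label. Second, total thyroidectomy or lobectomy was "performed in 158 (79.8%) and 40 (20.2%) patients", so most patients contribute two nerves.

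Other items are recorded by side ("Duration of lobectomy for each site, period of time for initial identification of RLN after the mobilization of upper pole on each site"). The latency item has no such wording, and neither document says how side enters any comparison.

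**The concern.** Latency after vagal stimulation depends on the length of the path. The left recurrent nerve loops lower than the right, so left vagal latencies should be longer on average. This is general anatomy; the documents do not state it or give a size. A per-nerve comparison that pools the sides then has two problems, and they pull in opposite directions.

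- The left-right gap is counted as random spread in the pooled SD, although in a two-sided patient it cancels from the comparison between arms. This makes the estimated standard error too large.
- Two nerves from one patient are correlated, and an independent-samples test ignores this. This makes the estimated standard error too small.

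At stake is the trustworthiness of the reported latency p-values. Depending on two unknown quantities, the test may declare a difference too readily or miss one that a suitable model would find.

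**Working it through.** The documents state no power, latency SD or left-right difference, so there is no design figure to reproduce.

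**Inputs from the documents.** 112 and 86 analysed patients; 158 two-sided and 40 one-sided operations; significance level 0.05, taken as two-sided.

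**Assumptions.** Within-side SD = 1. Left-right gap *d* = 0 to 3 SD. Within-patient correlation ρ = 0.3 to 0.5. True difference between arms 0.35 SD. The same share of two-sided operations in each arm, and left or right equally likely in lobectomies.

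**Nerves.** 158 × 2 + 40 = 356 at most. Split 112:86, this gives 112 × 356/198 = 201.4 and 86 × 356/198 = 154.6. The base standard error is b = √(1/201.4 + 1/154.6) = 0.1069.

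**Standard error that the pooled t-test estimates.** b√(1 + d²/4). The inflation factor is 1.03, 1.12, 1.41 and 1.80 for d = 0.5, 1, 2 and 3.

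**Actual standard error of the pooled difference.** b√(1 + (316/356)ρ + (40/356)d²/4). The 158 pairs add 158 × 2ρ = 316ρ, and the gap cancels within each pair. The 40 single nerves each keep d²/4.

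**Break-even.** The two are equal when d²/4 = ρ, that is d = 2√ρ: 1.10 SD at ρ = 0.3 and 1.41 SD at ρ = 0.5. Below this the error bars are too narrow, above it too wide.

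**False-positive rate** = 2[1 − Φ(1.967 × estimated/actual)]. **Power** = Φ((0.35 − 1.967 × estimated)/actual).

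Example, d = 2 and ρ = 0.3: estimated 0.1069 × 1.414 = 0.1512; actual 0.1069 × √(1 + 0.266 + 0.112) = 0.1255; ratio 1.20. The false-positive rate is 2[1 − Φ(2.37)] = 1.8%, and power is Φ((0.35 − 0.2974)/0.1255) = Φ(0.42) = 66%.

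| Gap (SD) | Estimated/actual SE, ρ 0.3 / 0.5 | False-positive rate | Power, pooled test |
|---|---|---|---|
| 0 | 0.89 / 0.83 | 8.1% / 10.2% | not comparable |
| 0.5 | 0.91 / 0.86 | 7.2% / 9.2% | not comparable |
| 1 | 0.98 / 0.92 | 5.3% / 7.0% | 83% / 81% |
| 2 | 1.20 / 1.13 | 1.8% / 2.6% | 66% / 65% |
| 3 | 1.46 / 1.38 | 0.4% / 0.6% | 41% / 42% |

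**With side and patient in the model.** SE = b√(1 + 0.888ρ) = 0.1203 or 0.1285. Power is Φ(0.35/0.1203 − 1.96) = 83% or Φ(0.35/0.1285 − 1.96) = 78%, whatever the gap.

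Simulation of the same structure agrees within its error. It puts the false-positive rate at about 6–10% for gaps of 0–0.5 SD and 5–8% at 1 SD, and pooled power at 40–43% at 3 SD. The model with side and patient-clustered standard errors kept the false-positive rate near 5%.

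**Both terms are needed.** In simulation, adjusting for side alone left the false-positive rate at about 8–11% for ρ of 0.3 to 0.6. Conversely, the covariance of two nerves about the pooled mean is ρ − d²/4, which turns negative once d exceeds 2√ρ. A patient effect without side therefore misreads the structure at large gaps.

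**The case against.** A reader might infer that pooling always inflates the standard error, so that a real latency difference will be missed. The figures do not support that. At a gap of 1 SD the pooled test has 83% or 81% power against 83% or 78% for the adjusted model. Its error bars are close to right or too narrow, and any apparent advantage comes from an excess of false positives. Loss of power appears only at gaps well above the break-even. Nor is the estimated difference biased in two-sided patients, where the gap cancels.

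Other objections also carry weight:

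- Pooling is inferred from silence. The SAP names no unit of analysis, and comparison by side is not excluded. Still, an unadjusted two-group test on nerves that carry a group label is the plain reading. If patient means were intended, the correlation problem goes away, but lobectomy patients still carry the gap: simulated power is about 69–72% at 2 SD and 57–61% at 3 SD.
- The gap is not in the documents. Its existence rests on general anatomy and its size on an assumed range. The path-length argument concerns mainly vagal latency; for RLN stimulation it is weaker, and no claim is made here about amplitude.
- Raw latency is neither the primary endpoint nor a named secondary one. Adverse EMG changes are defined in the CIONM technique section relative to each nerve's baseline, so a constant shift between sides does not carry into them, nor into RLN injury.

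The Mann-Whitney option is not a way out: ranks of the pooled nerves still mix sides and still treat paired nerves as independent.

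**Conclusion.** The point holds in a limited form. The plan leaves side and patient out of the raw latency comparisons, and a pooled per-nerve test then has an error rate set by two quantities that it does not address. Over the assumed ranges, the false-positive rate runs from about 10% (no gap, ρ = 0.5) to under 1% (3 SD gap). Power for 0.35 SD falls to about 66% at 2 SD and 41–43% at 3 SD, where the adjusted model has about 78–83%. The direction of the error cannot be settled from the documents.

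These sizes rest on the assumed gap, correlation and true difference, on per-nerve pooling, and on 356 nerves as the maximum. The consequence stays within the raw-latency comparisons. It is a minor matter of precision and validity and gives no reason to doubt the primary comparison.

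**What to change.** Add to the SAP that vagal latency, and RLN latency in the same way, is analysed per nerve, with group and side (left or right) as fixed factors and either a random patient effect or patient-clustered standard errors. Show latency summaries for left and right nerves separately in each arm. If ranks are preferred, compare the arms within each side, where a patient contributes at most one nerve.

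The cost is one degree of freedom for side and slightly more analysis work. No new data should be needed, since each latency belongs to a particular nerve; this assumes that the dataset records its side.
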